Assessment/activity	Treatment				Antibody response evaluation / EOT ^a	IPD ^b	FU / End of Study Visit	Unsch	Details in CSP Section or Appendix
Visit	V3	V4	V5	V6	V7		V8		
	W0	W4	W8	W12	W16		W28		
Visit window (days) ^c									
	± 0	± 3	± 3	± 3	± 3	± 3	± 3		
Inclusion and exclusion criteria	X								Sections 5.1 and 5.2
Randomization	X								Section 6.3.1
Complete physical examination	X				X	X	X		Section 8.2.1
Brief physical examination		X	X	X				X	Section 8.2.1
Vital signs	X	X	X	X	X	X	X	X	Section 8.2.2
CCI	█	█	█	█	█	█			
CCI	█	█	█	█	█	█	█	█	
Serum chemistry	X				X	X	X		Section 8.2.4
Hematology ^d	X				X	X	X		Section 8.2.4
Local urinalysis	X				X	X	X		Section 8.2.4
Urine pregnancy test (dipstick) ^e	X	X	X	X	X	X	X		Section 8.2.5.1
PK	X ^f			X ^f	X	X	X		Section 8.5.1
ADA	X ^f				X	X	X		Section 8.5.2
Serum antibodies to influenza virus				X ^g	X				
Administration of influenza vaccine ^h				X					Section 6.2.1.3
Administration of study intervention	X	X	X	X				X ⁱ	Section 6.2.1.3

Assessment/activity	Treatment				Antibody response evaluation / EOT ^a	IPD ^b	FU / End of Study Visit	Unsch	Details in CSP Section or Appendix
Visit	V3	V4	V5	V6	V7		V8		
	W0	W4	W8	W12	W16		W28		
Visit window (days) ^c									
	± 0	± 3	± 3	± 3	± 3	± 3	± 3		
Adverse Events	X	X	X	X	X	X	X	X	Section 8.3
Concomitant medication	X	X	X	X	X	X	X	X	Section 6.5

^a If influenza vaccine administration is delayed, unscheduled study intervention visits may occur prior to Visit 6 until the influenza vaccine is available at study sites. EOT assessments should be performed 4 weeks after last dose of study intervention.

^b If IPD visit occurs at the same time as the scheduled Visit 6 (Week 12), participants should perform all assessments, including influenza antibodies followed by influenza vaccination. Participants should then return to the study site for Visit 7 (Week 16) and perform all assessments, including influenza antibodies. Refer to CSP Section 7.1 for additional information.

^c All visits are to be scheduled from the date of randomization, not from the date of previous visit, except in the case of early discontinuation from study intervention (see Section 7.1 for details).

^d Eosinophils, basophil, and monocyte counts will be redacted from the central laboratory reports except at Visit 3 prior to study intervention administration.

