^e For women of childbearing potential only, urine HCG test to be completed at study site on each study visit (before study intervention administration on Visit 3 to Visit 6).

^f PK and ADA to be collected PRIOR to study intervention dose at Visit 3 and PK to be collected PRIOR to influenza vaccination at Visit 6.

^g Blood draw for serum antibodies to influenza vaccine should occur prior to administration of influenza vaccine. If influenza vaccine administration is delayed from Visit 6 (Week 12), pre-influenza vaccine blood draw for serum antibodies should only occur on the week of influenza vaccine administration.

^h Influenza vaccine is to be administered at a different site than study intervention and site of injection noted. Participant is to be observed for 15 minutes after injection and before administering study intervention. Influenza vaccine is to be administered after scheduled blood samples are taken and prior to study intervention administration.

ⁱ If influenza vaccine administration is delayed, an additional 1 to 2 unscheduled study intervention visits may occur prior to Visit 6, until the influenza vaccine is available at study sites. All assessments during the unscheduled visit may not be necessarily completed.

Abbreviations: **CCI** ADA=anti-drug antibodies; AE=adverse event; CSP=clinical study protocol; EOT=end of treatment; FU=follow-up; HCG=human chorionic gonadotropin; IPD=investigational product discontinuation; PK=pharmacokinetics; Unsch=unscheduled; V=visit; W=week.

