6.2.1.2 Dose Preparation

Prior to each study intervention administration at the study site:

- Investigator/authorized delegate will assess injection site as per standards of medical care.
- For women of childbearing potential, urine pregnancy test will be done; study intervention will be administered only when the result of the test is negative (see Section 8.2.5.1).

The APFS should be visually inspected prior to dose preparation. The study intervention will be provided to the study sites as a clear to slightly opalescent, colorless to light yellow liquid, practically free from particles contained in a pre-filled syringe to be stored between 36 °F to 46 °F (2 °C to 8 °C) until used.

If defects are noted with the study intervention, the investigator and site monitor should be notified immediately. Preparation of the study intervention must be performed by a qualified person (eg, pharmacist, investigator or nurse) at the site.

The study intervention does not contain preservatives and any unused portion must be discarded. Total in-use storage time from removal of the study intervention from the refrigerator to start of administration must not exceed 8 hours. If storage time exceeds this limit, a new dose must be prepared with a new study intervention kit.

To prepare the participant's dose, a study intervention kit will be selected for administration according to the kit identification number assigned by IWRS/IVRS.

Dose preparation steps:

- 1 Allow the study intervention to equilibrate to room temperature 68 °F to 77 °F (20 °C to 25 °C) for at least 60 minutes prior to dose administration. Ensure that the APFS is adequately protected from light during the warming process.
- 2 To prepare the study intervention for administration, remove the syringe from the carton by holding the middle of the syringe body.
- 3 Unwrap, but do not detach, the wrap-around label attached to syringe body to view the syringe contents.
- 4 Look at the liquid through the viewing window. The liquid should be clear to slightly opalescent, colorless to light yellow liquid, practically free from particles. Do not inject the study intervention if the liquid is cloudy, discolored, or contains large particles.
- 5 Re-wrap the label around the syringe body.

[figure not shown]

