8.2.5 Other Safety Assessments

8.2.5.1 Pregnancy Test

The following tests are applicable to female participants only and will be conducted at the timepoints specified in the SoA (Section 1.3).

- Serum β -HCG: To be done at screening Visit 1 only, for women of childbearing potential (analyzed at central laboratory).
- Urine pregnancy test: To be performed at the study center for women of childbearing potential at each treatment visit (before study intervention administration on Visit 3 to Visit 6) using a dipstick. A positive urine test result must be confirmed with serum β -HCG (analyzed at central laboratory).

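### Table 2 schedules a dose but no pregnancy test at unscheduled visits, which does not agree with the dosing section's requirement of a negative test before each dose

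*Protocol*

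**What the plan says.** **Extra doses.** Footnote i to Table 2 (Protocol Section 1.3) provides that, if vaccine is late, "an additional 1 to 2 unscheduled study intervention visits may occur prior to Visit 6". Section 6.6 repeats this. The Table 2 row "Administration of study intervention" is marked at Visits 3, 4, 5 and 6 and in the unscheduled column.

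**Pregnancy test in the grid.** The row "Urine pregnancy test (dipstick" is marked at Visits 3 to 7, at the discontinuation visit and at Visit 8. Its unscheduled cell is empty.

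**Footnote i on assessments.** It continues: "All assessments during the unscheduled visit may not be necessarily completed". It does not separate pre-dose checks from other assessments. SAP Section 3.3.3 repeats the allowance and adds nothing on pre-dose checks.

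**Footnote e, attached to the pregnancy test row.** For women of childbearing potential: "urine HCG test to be completed at study site on each study visit (before study intervention administration on Visit 3 to Visit 6".

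**Section 8.2.5.1.** It refers to the schedule for timepoints and places the urine test "at each treatment visit (before study intervention administration on Visit 3 to Visit 6".

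**Section 6.2.1.2.** Under the lead-in "Prior to each study intervention administration at the study site", it calls for a urine test in women of childbearing potential and says "study intervention will be administered only when the result of the test is negative". It makes no exception for unscheduled doses.

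**The concern.** Two parts of the protocol point a site in different directions at the same visit. The grid shows a dose with no pregnancy test beside it, and footnote i says not everything at that visit need be done. The dosing section makes the dose conditional on that test.

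What is at stake is participant safety and consistent conduct, not an estimate. Pregnancy is a reason to give no further study intervention (Section 7.1), and Section 8.3.10.1 calls for immediate discontinuation. Participants are 12 to 21 years old, and Section 5.3.4 counts a female adolescent as of childbearing potential from menarche or Tanner Stage 3. The protocol also expects that vaccine delay may happen: the synopsis, Section 4.1, Section 6.6 and Table 2 all provide for it.

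The dosing section does not settle the matter by itself in practice. Section 8 makes adherence to the schedule mandatory. The dosing row of Table 2 sends the reader to Section 6.2.1.3, whereas the pregnancy test condition sits in Section 6.2.1.2.

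**Working it through.** There is no statistic to reproduce. The check is a count of table cells, a comparison of text, and simple date arithmetic.

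**Step 1. Count the Table 2 marks.** The columns are Visits 3, 4, 5, 6, 7, discontinuation, Visit 8 and unscheduled.

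| Row | V3 | V4 | V5 | V6 | V7 | Disc. | V8 | Unsch. | Total |
|---|---|---|---|---|---|---|---|---|---|
| Study intervention | X | X | X | X | | | | X | 5 |
| Urine pregnancy test | X | X | X | X | X | X | X | | 7 |
| Vital signs | X | X | X | X | X | X | X | X | 8 |

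Dosing occurs in 5 columns and the test is marked in 4 of them. The unscheduled column is the exception. Vital signs, brief physical examination, adverse events and concomitant medication all keep their unscheduled marks, so the blank is unlikely to come from the way the table was read.

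**Step 2. Set the texts side by side for an unscheduled dosing visit.**

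| Source | Test before the extra dose? |
|---|---|
| Table 2 grid | Not marked |
| Footnote i | Silent on the test; allows assessments to be left incomplete |
| Footnote e | Opening words cover every study visit; the parenthesis names only Visits 3 to 6 |
| Section 8.2.5.1 | Opening words cover every treatment visit; the parenthesis names only Visits 3 to 6, and timepoints are those of the schedule |
| Section 6.2.1.2 | Required before each dose; no dose without a negative result |

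The grid and Section 6.2.1.2 do not agree. Footnote e and Section 8.2.5.1 do not resolve it. Their opening words reach the unscheduled visit, while the parenthesis, and in Section 8.2.5.1 the reference back to the schedule, can be read as excluding it.

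**Step 3. Size on the grid alone.** Inputs: four planned doses at Weeks 0, 4, 8 and 12 (Section 4.1); one or two extra doses before Visit 6 at 4-week intervals (footnote i, Section 4.1); end of treatment four weeks after the last dose, at Week 16, 20 or 24 (SAP Section 3.3.1). Visit 6, the last dosing visit, therefore falls at Week 16 − 4 = 12, 20 − 4 = 16 or 24 − 4 = 20.

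| Extra doses | Dose weeks | Grid-marked tests up to Visit 6 | Longest gap | Doses inside that gap |
|---|---|---|---|---|
| 0 | 0, 4, 8, 12 | 0, 4, 8, 12 | 4 weeks | none |
| 1 | 0, 4, 8, 12, 16 | 0, 4, 8, 16 | 16 − 8 = 8 weeks | 1 (Week 12) |
| 2 | 0, 4, 8, 12, 16, 20 | 0, 4, 8, 20 | 20 − 8 = 12 weeks | 2 (Weeks 12 and 16) |

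So 1 of 5 doses (20%) or 2 of 6 (33%) fall at a visit whose column shows no test. These are nominal weeks and ignore visit windows.

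**The case against.** The strongest reply is that the protocol already prohibits an untested dose. Section 6.2.1.2 applies to each administration, makes no exception, and refers across to Section 8.2.5.1. An empty cell cannot override an explicit condition for dosing. This stands. A reader might infer from the blank cell and footnote i that the protocol permits extra doses without a test; the documents do not support that.

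A reader might also infer that Section 8.2.5.1 omits the test at unscheduled dosing visits. That too goes too far. A visit held to give study intervention is, in ordinary language, a treatment visit. The parenthesis may only fix the order of test and dose at the scheduled visits. Footnote e supports this reading, because the same row also marks Visits 7 and 8 and the discontinuation visit, where no dose is given. These texts are ambiguous rather than silent.

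Footnote i does not mention pregnancy testing and may refer only to the assessments marked for that visit. The gaps calculated here arise only if vaccine is delayed and a site follows the grid alone. Contraception is separately required of the women concerned who are sexually active with a non-sterilized male partner (Section 5.3.4). All of this lowers the likelihood of harm. It does not remove the disagreement between the grid and the dosing section, and the need to choose between readings is itself the defect.

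**Conclusion.** The inconsistency holds. The unscheduled column is the one dosing column of five with no pregnancy test mark, footnote i loosens that visit without excepting pre-dose checks, and Section 6.2.1.2 requires a negative test before each dose. The consequence is a risk of oversight at sites; it is not a permission in the protocol.

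If vaccine is delayed and a site works only from the grid and footnote i, one dose falls in an 8-week gap between tests, or two doses fall in a 12-week gap. This assumes nominal visit timing and applies only to women of childbearing potential who receive extra doses. The documents give no forecast of vaccine delay, so the number affected cannot be estimated. No endpoint, analysis set, estimate or precision figure changes. The point deserves correction because it concerns participant safety and is cheap to put right.

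**What to change.** Reconcile Table 2 (the unscheduled column and footnotes e and i), Section 8.2.5.1 and Section 6.2.1.2 so that all of them state one and the same pre-dose pregnancy test requirement for unscheduled dosing visits. In footnote i, state how the allowance for incomplete assessments relates to pre-dose requirements. In footnote e and Section 8.2.5.1, make clear whether the parenthesis limits the visits or only fixes the order of test and dose. What the requirement should be is for the sponsor to decide; the request is that the passages agree.

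The cost is one table cell and some footnote and section wording. As a protocol change it needs the approvals described in Appendix C 1. Any effect on the amount of testing depends on the requirement the sponsor states. The statistical analysis needs no change.

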2 INTRODUCTION

This is a Phase 3b, multicenter, randomized, double-blind, parallel group, placebo-controlled study investigating the potential effect of tezepelumab on antibody responses following seasonal quadrivalent influenza virus vaccination.

2.1 Study Rationale

The epithelial cell-derived cytokine, TSLP, is produced in response to proinflammatory stimuli and drives allergic inflammatory responses, primarily through its activity on ILC-2, dendritic (Gilliet et al 2003, Soumelis et al 2002, Reche et al 2001) and mast cells (Allakhverdi et al 2007). Human TSLP expression is reported to be increased in asthmatic airways correlating with disease severity (Ying et al 2005).

Tezepelumab is a human mAb IgG2 λ directed against TSLP, expressed in a CHO CS-9 cell line. The molecule is a heterotetramer consisting of 2 heavy chains of the IgG2 subclass and 2 light chains of the lambda subclass, which are covalently linked through disulfide bonds. Tezepelumab binds with human TSLP and prevents its interaction with TSLP receptor complex. As a result, targeting TSLP may inhibit multiple biologic pathways involved in asthma (Gauvreau et al 2014).

In the Phase 3 NAVIGATOR and Phase 2b PATHWAY studies, tezepelumab reduced exacerbations compared with placebo in participants with moderate to severe, uncontrolled asthma, irrespective of baseline levels of T2 inflammatory biomarkers (blood eosinophil counts, fractional exhaled nitric oxide, and serum total IgE) (Corren et al 2017, Menzies-Gow et al 2021). In these studies, tezepelumab also improved lung function, asthma control and patient health-related quality of life in the overall population. In addition, in these studies, tezepelumab has been shown to decrease IgE levels; however, its administration did not affect IgG, IgM or IgA. In a preclinical toxicology study with cynomolgus monkeys the IgG response to keyhole limpet antigen was suppressed but only at doses much higher than used in human studies (50 mg/kg subcutaneously [SC] weekly) (Investigator's Brochure for tezepelumab).

Owing to its immunomodulating effect, it is important to determine if tezepelumab affects functioning of the immune system. In this study, a functional response of the immune system will be assessed by measuring antibody responses to the influenza vaccine in adolescents and young adults with moderate to severe asthma.

The influenza vaccine was chosen for this study as GINA Guidelines recommend yearly influenza vaccination for asthmatics, in particular those with moderate to severe disease. The Center for Disease Control also recommends yearly influenza vaccination for asthmatics (GINA, CDC Asthma 2021). Quadrivalent, inactive influenza vaccine containing 4 strains (2

for influenza A and 2 for influenza B) selected for the influenza season 2021/2022 for the northern hemisphere will be used ([FDA 2021](#)).

Immunogenicity will be assessed using 2 types of strain-specific assays (dual primary endpoint) detecting vaccine humoral response:

- Hemagglutinin inhibition (HAI) assay and microneutralization (MN) assay.

Hemagglutinin inhibition assay measures the ability of serum to block haemagglutination, which is the aggregation of red blood cells caused by influenza virus. The resulting haemagglutination inhibition antibodies titer is a correlate of protection for influenza virus that is accepted by many regulatory agencies. Microneutralization assay detect antibodies that directly neutralize virus ([Hannoun et al 2004](#), [Hobson et al 1972](#), [Krammer 2019](#)).

The dual primary endpoint includes seroconversion outcome measures (4-fold rise in titer and titer $\geq 1:40$) provided as response rates, and central measures of tendency for the immune response (geometric mean fold rises [GMFR] and geometric mean titers [GMT]) for the HAI and MN assay results. For the Influenza A H3N2-strain, only the MN assay will be performed owing to the known low hemagglutination effect of the strain ([Sicca et al 2020](#)).

In this study, a functional response of the immune system to the influenza vaccine will be assessed in adolescents and young adults with moderate to severe asthma. The rationale for selecting this population is based on the previous similar study with anti-IL5 biologic drug benralizumab in which humoral immune response was assessed in adolescent and young adult (12 to 21 years old) severe asthmatics ([Zeitlin et al 2018](#)). A total of 103 participants were randomized and received benralizumab (n=51) or placebo (n=52). There were no consistent differences in HAI or MN antibody responses 4 weeks after the inactive quadrivalent influenza vaccine administration between participants receiving benralizumab or placebo.

Participant entry will be stratified by age (12 to 17-year age group and 18 to 21-year age group) to ensure equitable distribution of treatment allocation for analysis.

In addition to the immune response to vaccine, the tezepelumab impact on [CCI](#) [REDACTED] number of exacerbations, serum trough tezepelumab concentrations, and anti-drug antibodies (ADAs) will be investigated.

2.2 Background

Asthma is a chronic inflammatory disorder of the airways caused by the interaction of genetic and environmental factors. It is characterized by widespread, variable, and reversible airflow obstruction, airway inflammation, excessive mucus production; and airway hyperresponsiveness that lead to recurrent episodes of wheezing, breathlessness, chest tightness, and coughing ([CSGA 1997](#)). Progressive pathologic airway remodeling and scarring

may occur in persistent asthma resulting in partially reversible or irreversible airway obstruction ([Pascual and Peters 2005](#)).

The etiology of asthma is thought to be multi-factorial, influenced by both genetic and environmental mechanisms. The majority of cases arise when a person becomes hypersensitive to allergens. Approximately 19 million adult patients and 5.5 million children under 18 years of age in the USA are thought to have asthma ([Asthma and Allergy Foundation of America 2017](#)). Worldwide, asthma currently affects approximately 339 million people ([Global Asthma Network 2018](#)); yearly asthma accounts for an estimated 9.8 million physician office visits, 1.6 million emergency room visits, and over 3500 deaths in the USA ([Asthma and Allergy Foundation of America](#)).

Tezepelumab is being developed for the treatment of moderate to severe, uncontrolled asthma. Approximately 5% to 10% of asthma patients have severe asthma (based on 2018 estimates [[Global Asthma Network 2018](#)]), which may be inadequately controlled by ICS and LABA combinations together with additional controller therapies ([Brightling et al 2008](#)). These patients are at risk of asthma exacerbations ([Tough et al 1998, Turner et al 1998](#)) and have the greatest medical need among the asthmatic population today. Patients with severe asthma represent the greatest economic cost (> 50% of total asthma-related health care costs; [Antonicelli et al 2004, Serra-Batilles et al 1998, Barnes and Kuitert 1996](#)).

Study D5180C00007 (NAVIGATOR) was a Phase 3, multicenter, global, randomized, double-blind, placebo-controlled study to assess the efficacy and safety of 210 mg tezepelumab administered SC Q4W for 52 weeks. The population of interest was adults and adolescents with severe, uncontrolled asthma between the ages of 12 and 80 years and both overall and across a broad spectrum of asthma phenotypes as determined by participants with blood eosinophils above and below 300 cells/ μ L, FeNO above and below 25 ppb, as well as allergic and non-allergic status. A total of 1061 participants were randomized in a 1:1 ratio to tezepelumab or placebo and 1059 participants (including 82 adolescents) received at least one dose of study intervention. Tezepelumab treatment resulted in a statistically significant and clinically meaningful reduction in annualised asthma exacerbation rate (AAER) by 56% ($p < 0.001$) compared with placebo in the overall population and by 41% compared with placebo in participants with baseline blood eosinophils <300 cells/ μ L ($p < 0.001$). The mean serum trough concentration of tezepelumab increased over time and approached steady state by 12 weeks. Treatment-emergent ADAs were detected at any time during the study in 4.9% (26) of participants treated with tezepelumab. Neutralizing antibodies to tezepelumab were detected in only one (0.2%) of the participants treated with tezepelumab. On-treatment AEs were similar between the placebo (80.8%) and the total tezepelumab (77.1%) dose groups and the majority of participants had on-treatment AEs that were mild or moderate in severity and not related to the study intervention. The percentage of participants who discontinued the trial regimen was 6.8% in the tezepelumab group and 10.7% in the placebo group. On-treatment

AEs that resulted in permanent discontinuation of study intervention was 2.1% in the tezepelumab group and 3.6% in the placebo group. Overall, tezepelumab was well tolerated with an acceptable safety profile and no safety signals in both adult and adolescent participants with severe, uncontrolled asthma ([Menzies-Gow et al 2021, TEZSPIRE FDA Prescribing Information 2021](#)).

For moderate to severe asthma patients who are uncontrolled on ICS, LABA and other controllers, biologic therapies may provide benefit. Omalizumab may be suitable for a subgroup of patients with proven reactivity to an aeroallergen and elevated serum IgE levels who remain inadequately controlled with ICS plus LABA ([XOLAIR US PI 2019, XOLAIR SmPC 2019](#)). Four additional biologics, mepolizumab, reslizumab, benralizumab, and dupilumab, have been approved for severe asthma with an eosinophilic phenotype and/or those requiring oral corticosteroid (OCS) therapy ([NUCALA SmPC 2019, NUCALA US PI 2019, CINQAERO SmPC 2021, CINQAIR US PI 2020, FASENRA SmPC 2019, FASENRA US PI 2019, DUPIXENT SmPC 2020, DUPIXENT US PI 2019](#)).

Biologics targeting IL-4, IL-5, and IgE are now included in international treatment guidelines ([GINA](#)) as add-on treatments to patients whose asthma remains uncontrolled with LABA/ICS treatment. However, even when using currently available biologics, substantial proportions of patients continue to experience exacerbations and may benefit from agents that target different molecular pathways ([Wenzel 2016, Froidure et al 2016, Swedin et al 2017](#)). Therefore, despite these additional therapeutic options, there is still a clear unmet medical need among patients with moderate to severe asthma, independently of IgE status or eosinophil level, who are unable to gain asthma control using currently available therapies.

Both GINA and CDC recommend annual influenza vaccines for children and adults with asthma because they are at high risk of developing serious flu complications, even if their asthma is mild or their symptoms are well-controlled by medication. Influenza can result in airway and lung inflammation which can contribute to acute asthma exacerbations. Asthma is the most common medical condition among children hospitalized with influenza and one of the more common medical conditions among hospitalized adults ([CDC Asthma 2021](#)). Recent systematic review and meta-analysis that included observational studies designs suggested that influenza vaccination reduced the risk of asthma exacerbations ([GINA 2021](#)).

Tezepelumab is currently being developed as a potential treatment option for the management of moderate to severe, uncontrolled asthma in adolescent and adult patients. By blocking TSLP, tezepelumab has been shown to have a broader impact on the inflammatory responses seen in asthma than other biologics.

Additional studies with tezepelumab have been completed. These include a mechanistic study (D5180C00013; CASCADE) conducted in adults with inadequately controlled asthma, an OCS sparing study (D5180C00009; SOURCE) conducted in adults with OCS-dependent asthma, an

at-home use study in adults and adolescents with severe asthma study (D5180C00011; PATH-HOME), and a Japanese long-term safety study in participants with inadequately controlled asthma (D5180C00019; NOZOMI).

A detailed description of the above-mentioned additional studies and chemistry, pharmacology, efficacy, and safety of tezepelumab is provided in the current Investigator's Brochure.

